Dose Escalation will be conducted in 2 stages: a single subject stage (Schedule A only) and a multiple subjects stage. In the single subject cohorts, cohorts 1 and 2, single subjects will be enrolled at dose levels anticipated to be lower than those at which adverse events related to AMG 673 will be observed. Multiple subject cohorts, starting with cohort 3, will enroll and the cohort size will be extended to 3-4 subjects per cohort. The Bayesian logistic regression model (BLRM) design will be used to guide dose escalation. The actual dose selected at each dose decision may be at or below the model's recommended dose as determined by the dose level review team (DLRT) after considering all information. Subjects will be assessed for dose limiting toxicities (DLTs) for the duration of their first treatment cycle (ie, 2 weeks from D1 for subjects who receive 2 doses and 4 weeks for subjects who receive 4 doses in Schedule A and 4 weeks

from D1 for subjects in Schedule B). Subjects who complete the DLT period may proceed to a higher dose level for the following treatment cycle after the next dose level has been deemed safe by the DLRT, after consultation with Sponsor, if no DLT was reported for that subject and no \geq grade 3 adverse event(s), deemed treatment related by the investigator, are reported for that subject.

Estimation of initial and target MTDs

For Schedule A, it is anticipated that at least 2 MTDs may be estimated, one for the initial dosing and one for the subsequent step dosing. Should the initial dose be limited by adverse events related to first dose effects, the second MTD for the target dose will be estimated after giving the initial dose at MTD (step dose). Each MTD will be estimated following the dose escalation guided by BLRM described above. A second dose step may also be implemented in a cycle if this was considered appropriate and necessary to allow further dose escalation. This second dose step would be performed the same way as described above. In this case, a third MTD would be estimated for the dose to be administered after the second dose step.

Schedule B will be initiated after preliminary safety data of AMG 673 in Schedule A (eg, MTD1 is estimated to be $\geq 72 \mu\text{g}$) become available and may be conducted in parallel with Schedule A per Sponsor's decision. The MTD for Schedule B will be estimated following the dose escalation described in [Section 6.2.1.1.2](#) and guided by BLRM described above.

Expansion Cohort

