AMG 673 will be manufactured and packaged by Amgen and distributed using Amgen clinical study drug distribution procedures. The Investigational Product Instruction Manual (IPIM), a document external to this protocol, contains detailed information regarding the storage, preparation, destruction, and administration of AMG 673. Please refer to [Section 6.2.1](#) and the IPIM for additional information.

NOTE: A nurse trained in emergency medicine or a physician must be available when the infusion of AMG 673 is started for immediate intervention in case of complications.

AMG 673 is supplied as a sterile, preservative-free lyophilized powder for IV administration after reconstitution with sterile water for injection (WFI). After reconstitution with 1.2 mL of sterile WFI, the 1 mg/mL AMG 673 drug product is formulated with ■ mM glutamic acid, ■% (w/v) sucrose, and ■% polysorbate 80, pH ■. The final container is a single-use, 6R glass vial and contains a target extractable amount of 1 mg AMG 673.

The intravenous solution stabilizer (IVSS) is supplied as a sterile solution in a 10-cc glass vial containing 10 mL deliverable product. The IVSS does not contain an active pharmaceutical ingredient and is a buffered, preservative-free solution (■ mM citric acid, ■ M lysine hydrochloride, ■% (w/v) polysorbate 80, pH ■). The IVSS is intended for pre-treatment of IV bags prior to dilution of AMG 673 drug product.

AMG 673 solution for infusion will be prepared in bags for IV infusion and delivered through infusion lines.

For Schedule A, the drug will be administered as short term IV infusions on D1 and D5 of each treatment cycle. Up to 2 additional infusions per cycle (D12/D19) may be administered. The treatment-free interval prior to start of the following treatment cycle will have a duration of 0 to 14 days (depending on treatment response), but may be extended to up to 7 weeks in case of prolonged marrow aplasia and aleukemic cytopenia after consultation with Sponsor. It may also be extended for up to 3 days from the planned duration if necessary for logistical reasons. The

DLRT may make recommendations on changes of the duration of the infusion-free interval for future cohorts after evaluation of PK data.

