implemented, there will be a 72-hour interval between the dose step(s) and enrollment of the next subject for the first 10 subjects who will receive step dosing.

The same guidance applies in case of intra-subject dose escalation, if applicable.

Intra-subject dose escalation should only occur if:

- the next dose cohort has been deemed safe by the DLRT
- after consultation with the sponsor
- no DLT is reported during or after completion of the DLT period for that subject
- no \geq grade 2 adverse events (deemed treatment related by the investigator) are reported during treatment for that subject.

See [Section 7.2.2](#) for details on assessments applicable in case of intra-subject dose escalation.

Following this, no more than 3 subjects should be enrolled into a cohort in 2 weeks.

Dose escalation decisions will be made based on the recommendation of the BLRM model and the DLRT review after considering all information. The estimate of MTD will use BLRM design. The model's estimated MTD dose is the dose with the highest probability of the target toxicity probability interval (TPI), but with a less than 0.25 probability of an excessive or unacceptable TPI. The target TPI is (0.20, 0.33), and TPIs of (0.33, 0.60) and (0.60, 1.00) are defined as excessive and unacceptable, respectively. See [section 3.4](#) for replacement of subjects.

Dose escalations will continue until either of the following occurs.

- No DLTs are observed on study and
 - Minimum of 6 treated subjects at highest planned dose level
- DLTs are observed on study and
 - BLRM repeats the recommendation of a dose level (minimum of 6 treated subjects) or
 - A maximum of 40 subjects are enrolled within a schedule. If fewer than 6 subjects are treated at the MTD, additional subjects beyond 40 may be enrolled to confirm safety and tolerability.

The MTD is defined as the highest dose level whose DLT rate has the highest probability of the target TPI, an excessive/unacceptable TPI of < 0.25 , and a minimum of 6 subjects have been treated at the MTD.

Expansion Cohort

At completion of the dose escalation cohorts within a schedule, additional subjects (up to 10) will be enrolled in a dose expansion cohort to gain further clinical experience, safety and efficacy data in subjects with AMG 673. The dose to be evaluated will be at or below the MTD estimated in the dose escalation cohorts.

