6.2.1.1.1 Schedule A

The drug will be administered as short term IV infusions (approximately 30 minutes to 3 hours) on D1 and D5 of each treatment cycle followed by an infusion-free interval prior to the start of the following treatment cycle. Up to 2 additional infusions on D12 and D19 of a cycle may be implemented by DLRM recommendation.

The planned dose levels for the dose escalation cohorts are: 0.05 µg, 0.15 µg, 0.45 µg, 1.5 µg, 4.5 µg, 9 µg, 18 µg, 36 µg, 72 µg, 110 µg, 160 µg, 240 µg, 360 µg and higher if MTD is not reached (testing doses higher than 360 µg will be done via a substantial amendment for EU). The MTD or highest tested dose (or doses, in case of dose step) will be administered in the dose-expansion cohort.

Table 2. Schedule A Planned Dose Escalation Schematic^a

Number of Subjects	Target Dose ^b
1 ^c	0.05 µg/infusion
1 ^c	0.15 µg/infusion
3-4 ^c	0.45 µg/infusion
3-4	1.5 µg/infusion
3-4	4.5 µg/infusion
3-4	9 µg/infusion
3-4	18 µg/infusion
3-4	36 µg/infusion
3-4	72 µg/infusion
3-4	110 µg/infusion
3-4	160 µg/infusion
3-4	240 µg/infusion
3-4	360 µg/infusion

^a actual doses for a cohort will be up to DLRM recommendation

^b intermediate dose level(s) may be evaluated as necessary

^c in case of occurrence of a drug related safety or efficacy signal as listed below, the BLRM design would be triggered

The infusion-free interval will have a duration of 0 to 14 days depending on treatment response and recovery of blood counts, but may be extended to up to 5 weeks in case of prolonged marrow aplasia and aleukemic cytopenia after consultation with the sponsor. It may also be extended for up to 3 days from the planned duration if necessary for

logistical reasons. The DLRT may recommend on changes of the duration of the infusion-free interval for future cohorts after evaluation of PK data.

Depending on the treatment response, the following scenarios are possible in the first treatment cycle (shown for a 2-week cycle – infusions on D1 and D5 as an example):

- Tumor assessment on day 14: Subjects who show no detectable leukemic blasts in bone marrow and in peripheral blood will start the next cycle at day 21. Subjects who show detectable leukemic blasts in bone marrow or blood will start the next cycle at day 15.

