The infusion-free interval may be extended up to a maximum of 7 weeks in case of insufficient recovery of peripheral blood counts (neutrophils < 500/ μ l, platelets < 20,000/ μ l without transfusion) after consultation with the sponsor. In case the infusion-free interval is extended to 42 days, a bone marrow assessment is recommended 4 weeks after the last infusion of a cycle. In the case this assessment shows leukemic infiltration of the bone marrow (\geq 5% blasts), treatment may be resumed immediately and start the next cycle on day 15.

For longer treatment cycles, refer to Schedule of Assessments ([Section 7.1](#)) for bone marrow assessments.

Subjects will be hospitalized for a minimum of 8 days from start of the first infusion in cycle 1 (ie, until at least 72 hours after start of the second infusion on day 5) and for a minimum of 72 hours following day 12 and day 19 doses in cycle 1. If the subject receives a second subsequent cycle of AMG 673 at the same dose, hospitalization will be for a minimum of 8 days from start of the day 1 dose (ie, at least 72 hours after the day 5 doses). In the absence of DLTs and SAEs, shorter hospitalization may be considered upon PI recommendation and Medical Monitor agreement during cycle 2. Hospitalization following day 12 and day 19 doses in cycle 2 and onwards will be at the discretion of the treating physician. For subjects receiving >2 cycles, hospitalization for cycle 3 onwards for all doses will be at the treating physician's discretion.

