6.2.1.1.3 Schedule A and B

Up to 12 treatment cycles can be administered to each subject as long as the subject is deriving benefit in the judgment of the investigator.

If the next higher dose is deemed reasonably safe by the DLRT, intra-subject dose escalation is allowed (see [Section 3.1](#)) and additional hospitalization and procedures are required (see [Section 7.2.2](#)).

Additionally, subjects will be hospitalized for a minimum of 72 hours under the following circumstances:

- after each dose step, if applicable
- after dose increase in case of intra-subject dose escalation

Subjects will be hospitalized for a minimum of 48 hours under the following circumstances:

- after re-start of treatment after an interruption due to adverse event

Approved

Subjects can be hospitalized for a longer time period at the discretion of the investigator. A nurse trained in emergency medicine or a physician must be available when the infusion of AMG 673 is started for immediate intervention in case of complications. The hospitalization period may be extended at the discretion of the investigator. During hospitalization periods, an immediately accessible emergency room with resuscitation equipment must be available.

Prior to hospital discharge, vital signs will be measured in order to detect possible signs and symptoms of cytokine release syndrome. If required for logistical reasons (eg, long travel times), subjects may be hospitalized the day before start of dosing (day -1) of any cycle for required PK samples.

The start time of infusion should be chosen carefully so as to avoid any interference or inconvenience with time points of safety assessments or PK/PD measurements. The site should record any unscheduled interruption of an infusion on the eCRF, and provide the start and stop date/time of the infusion.

AMG 673 should be administered through a central venous access at a constant flow rate. The drug should not be administered as a bolus. In the event that administration through a central venous access is not possible, AMG 673 may be administered through a peripheral venous line. The IPIM will have further information regarding drug preparation and administration for AMG 673.

The quantity administered, start date/time, stop date/time, and lot number of IP are to be recorded on each subject's eCRF.

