7.2.2 Treatment

Treatment begins on day 1 (cycle 1 day 1) when the first IV infusion of investigational product is administered to a subject.

In addition to the mandatory hospitalization period (see [section 6.2.1.1](#)), there will be at least twice weekly visits to the site during the treatment period. Weekly visits will apply during the infusion-free interval between 2 treatment cycles.

The following procedures will be completed during the treatment period at the times designated in the Schedules of Assessments ([Section 7.1](#)).

The results of the D1 laboratory tests taken prior to infusion start will not have to be available before starting treatment with AMG 673. Laboratory assessments that were done within 24 hours prior to treatment start do not need to be repeated at D1 prior to infusion.

- Hospitalization (see [section 6.2.1.1](#) for minimum required hospitalization times)
- investigational product infusions (See [Section 6.2.1.1](#) for details)
- Clinical evaluation
 - Physical examination as per standard of care. Physical examination findings should be recorded on the appropriate eCRF
 - ECOG performance status
 - Weight
- Vital signs (ie, blood pressure, heart rate, respiratory rate, and temperature)
- Pulse oximetry
- ECG triplicate measurement
- Laboratory assessments: hematology, chemistry, coagulation, urinalysis, and serum pregnancy test (females only)
- 
- AMG 673 PK sample collection
-  sample collection
- Bone marrow aspirate / biopsy
- Serious adverse event reporting
- Adverse event reporting
- Disease-related event reporting
- Documentation of concomitant and rescue medications
- CT scan or MRI (to be considered in case of CNS adverse event of grade ≥ 3 only, particularly in cases of confusion, disorientation or seizures)
- Receipt of protocol-required therapies
- For subjects to whom intra-subject dose escalation (see [Section 3.1](#)) applies:
 - ECG assessments should be performed as in cycle 1, regardless of actual study cycle
 - PK samples should be taken as in cycles 1 and 2, respectively, regardless of actual study cycle
 - All other assessments should be performed as per the schedule of assessments for the actual cycle.

Approved

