**10. Changes From Protocol-specified Analyses**

**Time to Progression endpoint in protocol refers to Event Free Survival, to address the Relapse/refractory AML subjects who are already in progressive state and never respond.**

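### Protocol Section 3.1 bars intra-subject dose escalation after a related grade 2 adverse event, the Synopsis and SAP 3.1 only from grade 3; the maximum infusion-free interval and some minimum hospital stays also conflict

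*Protocol*

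**What the plan says.** **Escalation gate.** Protocol Section 3.1 (Multiple Subject Cohorts) sets four conditions for intra-subject escalation: the DLRT has judged the next dose cohort safe, the sponsor has been consulted, the subject has had no DLT in or after the DLT period, and no event at or above "grade 2 adverse events (deemed treatment related by the investigator) are reported during treatment for that subject". The Synopsis (Dose Escalation Cohorts) gives the same permission with DLRT clearance, sponsor consultation and a no-DLT condition, but bars events at or above "grade 3 adverse event(s), deemed treatment related by the investigator, are reported for that subject". SAP 3.1 repeats the Synopsis wording.

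Section 6.2.1.1.3 says "If the next higher dose is deemed reasonably safe by the DLRT, intra-subject dose escalation is allowed" and points to Section 3.1. Section 7.2.2, in its item that opens "For subjects to whom intra-subject dose escalation", points there too. Neither document says which text governs if they differ.

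**Infusion-free interval, Schedule A.** In the Synopsis (Investigational Product) the interval "may be extended to up to 7 weeks in case of prolonged marrow aplasia and aleukemic cytopenia". In Section 6.2.1.1.1 it "may be extended to up to 5 weeks in case of prolonged marrow aplasia and aleukemic cytopenia". The same section later says: "The infusion-free interval may be extended up to a maximum of 7 weeks in case of insufficient recovery of peripheral blood counts", with thresholds of neutrophils below 500/µl and platelets below 20,000/µl without transfusion. All three require sponsor consultation.

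**Hospital stay.** Minimum stays on restart after an adverse event, after a Schedule B intra-subject dose increase, and for Schedule B beyond cycle 2 are stated in the Synopsis and again in Sections 6.2.1.1.2, 6.2.1.1.3 and 6.2.1.4 and Table 14. The values differ, as tabulated below.

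**The concern.** This is a first-in-human trial, and cytokine release syndrome (CRS) is the identified risk in Table 1. Whether a subject may receive a higher dose is a safety decision, and the documents give two eligibility rules for it. A site working from the Synopsis could propose a subject with a related grade 2 event for escalation, meet every condition stated there, and still depart from Section 3.1. The DLRT and the sponsor review the case under either text, but they too have two written thresholds.

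The interval and hospital-stay conflicts raise the same difficulty at lower stakes: the same conduct can comply with one section and deviate from another.

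**Working it through.** The check is a comparison of current text, not of the amendment log or the SAP summary of changes. The plan has no statistical figure to reproduce here.

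| Rule | One text | Other text | Difference |
|---|---|---|---|
| Related AE grade that bars escalation | ≥ 2 (Section 3.1) | ≥ 3 (Synopsis; SAP 3.1) | one grade |
| Maximum interval, prolonged aplasia and aleukemic cytopenia, Schedule A | 7 weeks (Synopsis) | 5 weeks (6.2.1.1.1) | 49 − 35 = 14 days |
| Minimum stay, restart after an AE | 48 h (Synopsis; 6.2.1.1.3) | 72 h (6.2.1.4) | 72 − 48 = 24 h |
| Minimum stay, intra-subject dose increase, Schedule B | 48 h (Synopsis) | 72 h (6.2.1.1.3, both schedules) | 72 − 48 = 24 h |
| Stay, Schedule B beyond cycle 2 | physician's discretion (Synopsis) | 48 h after each dose (6.2.1.1.2; Table 14, footnote a) | no fixed minimum vs 48 h |

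**Gate.** The two versions state one permission, with the same DLRT and sponsor steps, so they are alternative thresholds and not complementary rules. The question is whether the separate no-DLT condition already excludes the disputed subjects. It does not. Under Section 6.2.1.3, grade 2 CRS is a DLT only if it fails to resolve to grade 1 or lower within 7 days. A subject with related grade 2 CRS that resolves within 7 days, and no other event, passes the no-DLT condition. Section 3.1 then bars escalation, while the Synopsis and SAP 3.1 permit it.

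**Interval.** 5 × 7 = 35 days and 7 × 7 = 49 days. On days 36 to 49 a subject with prolonged aplasia is within the Synopsis limit and beyond the 5-week limit in Section 6.2.1.1.1. The later 7-week sentence in that section has a different trigger, insufficient count recovery, which can overlap with the first. The 42-day allowance for grade 4 neutropenia in Section 6.2.1.4 is an exception to a discontinuation rule and is not counted as a conflict.

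**Stay.** For a Schedule A dose increase the Synopsis refers to first-cycle guidance, so the 24-hour conflict there is confined to Schedule B. For Schedule B beyond cycle 2, Section 6.2.1.1.2 does allow a shorter stay, but only without DLTs or SAEs, on the investigator's recommendation and with Medical Monitor agreement. The Synopsis attaches none of these conditions.

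**The case against.** The strongest reply is that the body of the protocol has one gate. Sections 6.2.1.1.3 and 7.2.2 both send the reader to Section 3.1, and following it also satisfies the Synopsis, since neither text obliges anyone to escalate. SAP 3.1 copies the Synopsis and is not an independent dosing rule, so the real conflict is Synopsis against body. DLRT clearance and sponsor consultation apply in either case. This stands as mitigation. It does not remove the conflict: the pointers suggest which text is operative, but nothing says so, and the Synopsis sentence reads as a complete rule.

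SAP Section 10, whose only entry is "Time to Progression endpoint in protocol refers to Event Free Survival", is silent on the gate. That section covers changes to analyses, so its silence is weak evidence, and the point does not need it.

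On the interval, a subject whose counts meet the thresholds in the later sentence of Section 6.2.1.1.1 may go to 7 weeks under that section. The days 36 to 49 conflict with the body therefore applies in practice to aplasia or cytopenia outside those thresholds. The Synopsis design text also refers to Section 6.2.1.1.1 for extensions, and both places add up to 3 days for logistics, so day 35 is not a sharp cutoff. These points narrow the consequence, but the same condition still carries two stated maxima.

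On hospital stay, all the figures are minimums and investigators may extend any stay, so the longer one satisfies both texts. These items weigh less than the gate.

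**Conclusion.** The concern holds. The threshold for offering a subject a higher dose is stated in two incompatible ways, one grade apart, and the no-DLT condition does not close the gap. This is the main point and should be fixed.

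The secondary conflicts also hold: 14 days on the Schedule A interval for prolonged aplasia, 24 hours on restart after an adverse event (both schedules), 24 hours after a Schedule B dose increase, and no fixed minimum against 48 hours per dose for Schedule B beyond cycle 2.

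The limits are clear. The gate governs later-cycle dosing only and does not change DLT evaluability. The number of subjects affected cannot be estimated, because the documents give no rate of subjects whose worst related event is grade 2. The conclusion assumes only that the Synopsis, the body and the SAP are all current text.

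**What to change.** Reconcile the passages:

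- State one adverse-event threshold for intra-subject escalation in the Synopsis, Section 3.1 and SAP 3.1.
- State one maximum infusion-free interval for each condition in the Synopsis and Section 6.2.1.1.1, and say how the aplasia and count-recovery triggers relate.
- State one minimum stay on restart after an adverse event, one after a Schedule B intra-subject dose increase, and one rule for Schedule B beyond cycle 2, in every place where they appear.
- As a clarification, not a contradiction: align the grade 2 CRS wording in Section 6.2.1.4, Table 5 and the restart text of Section 6.6, so that it is clear whether an infusion in progress is stopped and how the 72-hour restart criterion then applies.

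Which values are kept is for the sponsor's clinical team. The cost is amendment wording and matching SAP text, with no extra patients or procedures.

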Dose escalation for the initial dosing MTD (MTD1) will proceed using 2 parts, single subject cohorts and multiple subject cohorts. In the single subject cohorts, single subjects will be enrolled at dose levels anticipated to be lower than those at which adverse events related to AMG 673 will be observed. When an adverse event related to first dose effects is observed, the cohort size will be extended to N = 3 to 4 subjects.

When the initial DLT is observed, the BLRM design will be used to guide dose level selection. After each cohort, the model's recommended MTD dose level for evaluation is the dose level with the highest probability of the target toxicity probability interval (TPI), but with a less than 0.25 probability of an excessive or unacceptable TPI. The actual dose selected at each dose decision may be at or below the model's recommended dose as determined by the dose level review team (DLRT) after considering all information.

The dose escalation will be stopped when any of the following occurs:

- A minimum of 6 subjects have been treated at the MTD1 level
- When the sample size reaches 40 subjects
- Or as determined by the DLRT after considering all information.

MTD2 (Schedule A)

Dose escalation for the MTD following the initial dosing (MTD2) will proceed after MTD1 is determined and implements a dose step. The cohort for which a dose step will be implemented will start treatment for the first dose at the MTD1 assessed in the dose escalation for the first MTD. After this run-in dose, there may be a dose increase to the next higher dose as per the dosing schedule shown in [Figure 2](#) of the protocol. If this treatment schedule is tolerated, following dose cohorts will continue to receive the run in (initial) dose at MTD1 to assess the MTD2. The target (2nd) dose will be increased until a MTD2 is reached. Dose escalation for the target (2nd) dose will be guided in the same way by the BLRM and the DLRT review after considering all information. An additional step may be added and the DLRT may determine MTD3 based on the same rules.

MTD Schedule B

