3.4 Replacement of Subjects

Ineligible subjects (ie, subjects who were exposed to investigational product [IP] but post hoc were found to be ineligible) may be replaced. During dose escalation, subjects that are not DLT-evaluable may be replaced (see [Section 6.2.1.3](#) for definition of a DLT-evaluable subject).

For Schedule A, a subject is not DLT-evaluable if he/she drops out earlier than 1 week after the last planned infusion (eg, day 5 or day 19, depending on the cohort) in cycle 1 for reasons other than an AE. All available safety data for subjects who are not DLT-evaluable will still be evaluated and considered in DLRM recommendations. A cycle will be considered complete and the subject will be DLT-evaluable if the subject has received IP treatment as planned (ie, infusions on D1, D5, and D12/D19 if applicable) and has remained on study for at least 1 week after the last dose in cycle 1.

For Schedule B, a subject must complete the 28 day DLT window and is not DLT-evaluable if they have not completed at least 70% of planned target doses in cycle 1 for reasons other than a DLT.

Exception: If a subject has completed treatment as planned but drops out of study earlier than described above due to progressive disease, they will still be considered DLT-evaluable and will not be replaced.

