6.2.1.3 Dose-cohort Study Escalation and Stopping Rules, Dose Limiting Toxicities (DLTs)

A DLT will be defined as any of the events described below occurring in a subject during the DLT window, unless clearly attributable to causes other than AMG 673. The DLT window for Schedule A will start on D1 (start of the administration of the first infusion) and last for 14 days for cohorts receiving 2 doses (ie, day 1 and day 5 dose) and for 28 days for subjects receiving 4 doses (ie, days 1,5,12,19). The DLT window for Schedule B will start on D1 (start of the administration of the first infusion) and last for the duration of cycle 1 and 2 (ie, 28 days). The CTCAE (version 4) will be used to assess will be used to assess toxicities/adverse events with the exception of CRS (see [Table 5](#) for grading of CRS).

DLT Evaluation

A subject is not DLT-evaluable if he/she drops out before completion of the DLT window for reasons other than an AE. All available safety data for subjects who are not DLT evaluable will still be evaluated and considered in DLRM recommendations. A subject will be DLT-evaluable if the subject has received the minimum cycle 1 doses planned for the respective cohort defined below:

- Schedule A : 2 doses with a 14-day DLT window, or 4 doses with 28-day DLT window
- Schedule B: completed $\geq 70\%$ of the planned target doses (eg, 10 doses out of a 14-day cycle 1 for cohort 1, at least 9 doses of the 12 planned at target dose cohort 2, etc) with 28-day DLT window

Exception: If a subject has completed treatment as planned but drops out of study before completing the DLT window due to progressive disease, they will still be considered DLT-evaluable and will not be replaced. The DLT window may also be extended retrospectively to assess events starting or persisting outside the window in case the DLT definition is time dependent (eg, in case of neutropenia, see below).

Any adverse event occurring outside the DLT window that is determined by the investigator to be possibly related to the investigational product, which is seen more frequently or is more severe than expected or is persistent despite appropriate

management, can be determined to be a DLT upon unanimous decision by the DLRT after review of the adverse event and all available safety data.

Events to be considered as DLTs and exceptions are listed below:

- Any treatment-related death

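### The six-subject minimum for the MTD counts subjects treated, not DLT-evaluable subjects, so an MTD can be declared with fewer than six evaluable subjects at the dose

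*Protocol*

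**What the plan says.** The minimum of six appears in six places, each time counted in treated subjects:

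- Protocol 3.1, MTD1 stopping rule: "A minimum of 6 subjects have been treated at the MTD1 level".
- Protocol 3.1, stopping rule when no DLT has been seen: "Minimum of 6 treated subjects at highest planned dose level".
- Protocol 3.1, stopping rule when DLTs have been seen: a repeated BLRM recommendation, again with six treated.
- Protocol 3.1, the clause allowing enrolment beyond 40 if fewer than six have been treated at the MTD.
- Protocol 3.1, MTD definition: "a minimum of 6 subjects have been treated at the MTD".
- SAP section 5, MTD definition, in the same words.

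DLT-evaluable is a separate status. Protocol 6.2.1.3 states: "A subject is not DLT-evaluable if he/she drops out before completion of the DLT window for reasons other than an AE". It also requires a minimum number of cycle 1 doses. On replacement, section 3.4 says: "During dose escalation, subjects that are not DLT-evaluable may be replaced". Cohort size is given in section 3.1 as a maximum of four evaluable subjects, with no lower limit in that sentence.

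The final MTD and RP2D estimate is to use all DLT-evaluable subjects from escalation and expansion (protocol 3.1 and SAP 3.1, Expansion Cohort).

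On intra-subject escalation, the synopsis says that subjects who complete the DLT period "may proceed to a higher dose level for the following treatment cycle", provided they had no DLT and no related adverse event above a stated grade.

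**The concern.** The minimum and the data it is meant to secure are counted in different units. A subject who leaves early for a reason other than an adverse event, or who receives too few cycle 1 doses, still counts as treated but adds nothing to a DLT-evaluable estimate.

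Subjects escalated into the dose raise a second question. Under section 6.2.1.3 the DLT window starts at a subject's first infusion, so these subjects have no defined DLT window at the new dose. They were allowed to escalate because they had tolerated a lower dose. The text neither includes them in the six nor excludes them.

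Estimating the MTD is a primary objective of this first-in-human trial. If the count is met without the intended DLT information, the declared MTD rests on less local evidence than a reader of the minimum would assume.

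**Working it through.** **1. The plan's own figures.** The synopsis gives the probability of at least one DLT as 27–70% with 3 subjects and 34–80% with 4, for true rates of 10–33%. With P = 1 − (1 − p)^n:

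- n = 3: 1 − 0.90³ = 27.1%; 1 − 0.67³ = 69.9%.
- n = 4: 1 − 0.90⁴ = 34.4%; 1 − 0.67⁴ = 79.8%.

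These reproduce. The documents give no such figure for the six-subject minimum.

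**2. The same formula at six, four and three evaluable subjects.** The values 4 and 3 are scenarios taken from the cohort size; the wording itself sets no floor.

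| Evaluable at the dose | P(no DLT) at 33% = 0.67^n | Upper one-sided 95% bound after no DLT = 1 − 0.05^(1/n) |
|---|---|---|
| 6 | 9.0% | 39.3% |
| 4 | 20.2% | 52.7% |
| 3 | 30.1% | 63.2% |

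**3. How often six treated would yield so few.** The non-evaluable share is not in the documents. Assume it is r, independent between subjects, with no replacement, and write q = 1 − r. Then P(at most 4 of 6 evaluable) = 1 − q⁶ − 6q⁵r. Subtracting a further 15q⁴r² gives P(at most 3).

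| Assumed r | At most 4 evaluable | At most 3 evaluable |
|---|---|---|
| 10% | 11% | 2% |
| 20% | 34% | 10% |
| 30% | 58% | 26% |
| 40% | 77% | 46% |

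This covers non-evaluability only. Counting escalated subjects would add to it.

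**4. Does the overdose limit enforce a minimum?** A two-parameter BLRM was run for Schedule B as an illustration. It used the stated prior constraints, with prior centres of 0.05 at 72 µg and 0.30 at the reference dose (from the SAP's summary of changes). The reference dose (160, 240 or 360 µg) and zero prior correlation were assumed, with no DLT among 3 or 4 subjects at each lower dose. The posterior probability of a DLT rate above 0.33 at the reference dose, to be compared with the limit of 0.25, was:

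- 0 of 3 or 0 of 4: 0.05–0.10, passes.
- 1 of 3: 0.32–0.35, fails.
- 1 of 4: 0.24–0.26, borderline.
- 1 of 6: 0.12–0.14, passes.

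So the limit tightens once a DLT is seen in few subjects, but it does not stop a dose with three or four DLT-free evaluable subjects.

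**5. Can the count be made in evaluable subjects today?** Two points stand in the way.

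- For Schedule A, section 3.4 sets the cut-off at 1 week after the last planned infusion, that is day 5 + 7 = 12 or day 19 + 7 = 26. Section 6.2.1.3 requires completion of the 14- or 28-day window.
- SAP section 6 defines no DLT-evaluable set. SAP 9.6.1 places the BLRM fit under the Safety Analysis Set by default, whereas SAP 3.1 bases the final estimate on DLT-evaluable subjects.

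**The case against.** The strongest reply is that six treated is an exposure minimum set beside a model-based estimate, and that other controls carry the weight. The MTD must have the highest target-interval probability and less than 0.25 probability of an excessive or unacceptable rate. Once DLTs occur, the stopping rule also asks for a repeated recommendation. The DLRT reviews all data, including those from non-evaluable subjects. The final estimate uses DLT-evaluable subjects, and the BLRM borrows across doses. All of this stands, and the minimum is not the only guard. But none of these controls fixes a number of evaluable subjects at the dose. Expansion need not supply them: the synopsis makes it optional, and the expansion dose may be below the MTD.

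Non-evaluability is also narrower than it may look. Dropout due to an adverse event falls outside the definition, and subjects who complete treatment and then leave for progression remain evaluable. That is fair, and it is why the frequencies in step 3 are only a range under assumption.

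Three stronger readings are tempting, and the documents do not support them:

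- **That escalated subjects do count towards the six.** No text says so. Section 3.1 speaks of a dose level administered to a cohort, which leans towards cohort assignment. This is an ambiguity.
- **That escalated subjects carry no information.** Section 3.1 brings DLTs after the DLT period into the BLRM, and section 6.2.1.3 lets the DLRT classify a later event as a DLT by unanimous decision.
- **That a clearly too toxic dose would be accepted whenever few subjects show 0 or 1 DLT.** That is not the declaration rule; in the illustration 1 of 3 fails the overdose limit.

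**Conclusion.** The point holds as a mismatch of counting units. The wording permits an MTD with fewer than six DLT-evaluable subjects at the dose, and leaves open whether escalated subjects can help fill the six.

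Its size is best shown by the zero-DLT comparison: going from six evaluable subjects to four or three raises the chance of missing a true 33% DLT rate altogether from 9% to 20% or 30%. That is exact binomial arithmetic for independent subjects at one dose, and it ignores information borrowed from other doses. How likely such a shortfall is cannot be derived from the documents. The BLRM results rest on an assumed reference dose and zero correlation; they serve only to show that the overdose limit does not replace a minimum.

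**What to change.** In all six places (the MTD1 stopping rule, both general stopping bullets, the beyond-40 clause and the MTD definition in protocol 3.1, and the MTD definition in SAP section 5), count DLT-evaluable subjects assigned to that dose level in cycle 1 instead of subjects treated. State that subjects escalated into a dose do not count towards the six. Their late DLTs can still enter the BLRM as section 3.1 provides.

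For the count to work:

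- Reconcile the Schedule A definitions of DLT-evaluable in sections 3.4 and 6.2.1.3.
- Define a DLT-evaluable analysis set in SAP section 6 and name it for the BLRM fit in SAP 9.6.1.

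The cost is an occasional replacement subject at the MTD and the time to enrol that subject. Section 3.4 already permits replacement, and the beyond-40 clause already permits the extra enrolment.
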